7 STUDY OBJECTIVES

Primary

- To evaluate the safety and tolerability of MOTREM in patients with septic shock

Secondary

- To evaluate the effects of MOTREM exposure over up to 5 days in patients with septic shock
- To evaluate the PK/PD and dose/PD relationships to TREM-1 pathway related markers
- To evaluate the effect of MOTREM on transcriptomics
- To evaluate the effect of MOTREM on clinical parameters (e.g. vasopressor doses, vasopressor-free days, ventilator-free days, mortality)

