11.3.2 Treatment Period (Day 1 to Day 4)

During the treatment period of up to 5 days, the following assessments will be performed daily (approximately at the same time of day):

- Concomitant therapy
- SOFA score
- Vital signs
- ECG
- Vasopressor use
- Invasive mechanical ventilation
- Intubation
- Mortality
- Adverse events
- Blood sample for ABG and P/F
- Blood samples for laboratory tests (according to schedule provided in Table 2):
 - Clinical Laboratory
 - Pharmacokinetics
 - Biomarkers
 - RNA profile
 - Plasma samples for retention (Day 1 only)
- Continued treatment with MOTREM i.v. (according to Table 5 or Table 6)

11.3.3 End of Infusion/Day 5

Patients will be treated until 12 (± 2) hours after the resolution of their septic shock (defined as vasopressor withdrawal) with a maximum treatment of 5 days (120 (± 2) hours). An

interruption of vasopressor treatment of up to 6 hours is permitted and not considered vasopressor withdrawal).

Patients may also be withdrawn from treatment for other reasons (see section 9.5).

At the end of treatment, the i.v. infusion will be stopped and the following assessments will be performed:

- Concomitant therapy
- SOFA score
- Vital signs
- Weight
- ECG
- Vasopressor use
- Invasive mechanical ventilation
- Intubation
- Mortality
- Adverse events
- Blood sample for ABG and P/F
- Blood samples for laboratory tests (according to schedule provided in Table 2):
 - Clinical Laboratory
 - pharmacokinetics
 - biomarkers
 - RNA profile

If the treatment is stopped any day before D5, the assessments listed above will be performed only once the day of the end of infusion.

For all patients alive, the SOFA score will however be calculated until day 5, no matter when the study treatment stopped. This data will be collected to the extent available in source data and analysed post-hoc (see section 15.5).

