12.8 Requirement of Vasopressor, Mechanical Ventilation and Intubation

The beginning and end of study of vasopressor therapy, invasive mechanical ventilation and intubation will be documented in the eCRF.

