15.1.3 Endpoints

Safety and tolerability will be the primary endpoint and it will be monitored during the course of the study as specified below:

Safety and Tolerability Parameters

- Vital signs: systolic (SBP) and diastolic (DBP) blood pressure, heart rate, and body temperature.
- ECG (12-lead ECG)
- Safety laboratory tests: haematology, coagulation, plasma biochemistry.
- Presence of anti-LR12 antibodies
- Adverse events: from screening until study completion.

Secondary endpoints include the following:

Pharmacokinetics

Plasma concentrations of LR12 will be measured by a validated LC-MS/MS assay and analysed using non-compartmental methods to obtain estimates of the PK parameters.

Pharmacodynamics (exploratory)

The concentration profiles of biomarkers (sTREM-1, immune and vascular related biomarkers) over time and biomarker mRNA levels will be analysed.

Clinical Parameters

- Resolution of organ dysfunction (SOFA score total and individual domains)
- Vasopressor use
- Invasive mechanical ventilation
- Renal support
- Time until shock reversal defined as cessation of vasopressor support for 24 hours
- Mortality at day 28 and day 90

Safety and tolerability will be the primary endpoint and in addition, the exposure of MOTREM will be analysed. The biomarker concentration profiles over time and the area under the concentration (AUC) curves will be analysed as secondary PD variables.

The MOTREM concentration profile over time and the main derived PK parameters will be analysed as PK endpoints.

The endpoints and their analysis will be further specified in the statistical analysis plan (SAP).

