15.1.5 Safety Analyses

Adverse events will be coded using the MedDRA dictionary version 18.1 or higher. Treatment emergent adverse events (events start after the first dose of investigational treatment or events present prior the administration of investigational treatment and worsened during the study (increased in severity)) will be classified by primary system organ class, preferred term and treatment group. Separate summaries will be performed for study medication related events, death, serious adverse events, adverse events leading to discontinuation of study medication and other adverse events of interest.

Other safety parameters that will be assessed include safety laboratory parameters (haematology, coagulation, biochemistry, arterial blood gases etc), vital signs (SBP, DBP, heart rate and body temperature), ECG and exposure of MOTREM. The parameters will be listed by treatment group (Placebo, Dose level 1, Dose level 2 and Dose level 3), patient and visit and summarised using standard descriptive statistics. All abnormal values will be identified in patient data listings. Changes from baseline will be described.

PD Analyses: Pharmacodynamic data will be listed by treatment, patient, and visit/time. Summary statistics will be provided by treatment and visit/time. Geometric means and CV will be presented for the primary and secondary PD endpoints.

PD endpoints will be compared between treatments with an ANOVA on logs. Each MOTREM dose group will be compared to placebo with a contract t-test at the 2-sided 10% level.

PK Analyses: Observed MOTREM serum concentrations will be summarised by treatment and corresponding time when sampling occurred. Derived PK parameters will be summarised by treatment.

Clinical Analyses: Several clinical parameters as the clinical events related to sepsis and its complications, the SOFA score total and each sub-score (respiratory, cardiovascular, hepatic, coagulation, renal and neurological system), the vasopressor use, the mechanical ventilation and intubation will be described by treatment group and visit. Standard descriptive statistics will be used.

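### Vasopressor-free and ventilator-free days are named in the objective but never defined or analysed, and the by-visit description given instead can compress vasopressor differences between arms

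*Combined protocol and SAP*

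**What the plan says.** **Objective.** Section 7, repeated in the synopsis, sets as a secondary aim: "To evaluate the effect of MOTREM on clinical parameters (e.g. vasopressor doses, vasopressor-free days, ventilator-free days, mortality".

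**Endpoints.** Section 15.1.3 lists vasopressor use and "Invasive mechanical ventilation" with no metric, time window, or rule for death or restart. It also lists "Time until shock reversal defined as cessation of vasopressor support for 24 hours" and "Mortality at day 28 and day 90". Free days are not mentioned.

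**Analysis.** Under the clinical analyses in 15.1.5, "the vasopressor use, the mechanical ventilation and intubation will be described by treatment group and visit", using standard descriptive statistics. That sentence does not name shock reversal. Section 15.1.1 leaves missing clinical data unreplaced.

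**Visits.** Section 11.3.3 states: "Patients will be treated until 12 (± 2) hours after the resolution of their septic shock (defined as vasopressor withdrawal", with a ceiling of 120 (± 2) hours. It adds: "If the treatment is stopped any day before D5, the assessments listed above will be performed only once the day of the end of infusion". Day 10 (11.3.6) covers only anti-drug antibodies and the direct Coombs test. The next visit with vasopressor and ventilation assessments is Day 28 ± 2 (11.3.4).

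**Records.** Section 12.8: "The beginning and end of study of vasopressor therapy, invasive mechanical ventilation and intubation will be documented in the eCRF". Section 12.10 records date and time of death to Day 90.

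**The concern.** A free-days measure counts time alive and off support over a fixed window, for every patient. A by-visit description is a series of snapshots, and here the snapshots stop soon after the patient comes off vasopressors. A patient with a daily vasopressor record on Days 1 to 5 is, by design, either still on vasopressors or no more than about 14 hours off them. Patients weaned earlier have left the visit schedule, and so have those who died. If the denominator is whoever was assessed that day, it is selected by the outcome being described.

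Section 6.3 says the data will help design subsequent studies. A real shortening of vasopressor support could look small in these tables, and the two free-days quantities that the objective names would have no stated result.

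**Working it through.** **1. Group size.** Stage 1: 3 cohorts × (3 active + 1 placebo) = 12. Stage 2: 4 arms × 9 = 36. The total is 48, as stated. Each dose has 3 + 9 = 12 and placebo has 3 × 1 + 9 = 12, matching section 15.2. The plan gives no effect size or power for any clinical parameter, so there is no such figure to reproduce.

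**2. What follows from the text alone.**
- A patient whose infusion ends because shock resolved is off vasopressors at the end-of-infusion visit by construction, barring a restart in those 12 hours. The share on vasopressors at that visit is 0% in any arm for such patients.
- From the end of infusion (about Day 5 at the latest) to Day 28, no visit records vasopressor use or ventilation. Visit data alone therefore cannot give free days to Day 28.
- Section 11.3.3 makes an explicit exception for SOFA, to be scored to Day 5 whenever treatment stopped. Section 15.5 explains that such SOFA data had been treated as missing, and it retrieves only SOFA and ICU stay.

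**3. Illustrative size for vasopressors.** Assumptions not in the documents: exponential time T to withdrawal, medians 36 h and 72 h, no deaths, infusion ending exactly 12 h after withdrawal, and a denominator of patients still assessed.
- All patients on vasopressors at t: P(T > t) = 2^(−t/median).
- Still assessed at t: P(T > t − 12).
- On vasopressors among those assessed: P(T > t) / P(T > t − 12) = 2^(−12/median), which does not depend on t.

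| | Median 36 h | Median 72 h | Difference |
|---|---|---|---|
| All patients, 72 h | 2^(−2) = 25% | 2^(−1) = 50% | 25 points |
| Still assessed at 72 h | 2^(−60/36) = 31% | 2^(−60/72) = 56% | 25 points |
| On vasopressors among assessed | 2^(−12/36) = 79% | 2^(−12/72) = 89% | 10 points |
| All patients, 120 h | 10% | 31% | 21 points |

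With 12 per arm, the 72 h row of the table would show about 3.0 of 3.8 patients against 6.0 of 6.7.

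**4. Range.** A simulation (400,000 patients per scenario; 30% mortality, deaths uniform over 28 days; infusion ending 10 to 14 h after withdrawal or at 120 h) used median times to withdrawal of 24, 48 and 72 h. Among patients still attending, the share on vasopressors is flat over Days 1 to 4, at about 71%, 84% and 89%. Among all patients alive it falls from 50% to 6%, 71% to 25% and 79% to 40%. The time course is lost, while some difference between arms remains.

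**5. Ventilation.** The stop rule depends on vasopressor withdrawal, not extubation. In the same simulation (every patient ventilated, extubation following withdrawal), the share still ventilated at a rule-triggered end of infusion is 71%, 84% and 92% for extubation lags with medians of 24, 48 and 96 h, so the rule does not fix it. The selected denominator still matters. With a 48 h lag, about 98% to 99% of patients assessed at Day 4 are ventilated, against 44%, 60% and 69% of those alive. These figures lean heavily on assuming that extubation always follows withdrawal.

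**The case against.** The strongest reply has four parts.

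- **Other endpoints serve the objective.** The objective is a list of examples and includes mortality, which is an endpoint. Time until shock reversal would show a drug that shortens vasopressor support. Because it needs 24 hours off vasopressors while infusion ends at 12 (± 2), it must come from records beyond the infusion visits. This stands, with two limits: 15.1.5 does not name shock reversal in its analysis, and neither measure covers ventilation.
- **The denominator is inferred.** Section 15.1.5 does not say that weaned patients drop out, and the start/stop records would allow status to be assigned to everyone. This stands. The inference rests on 11.3.3, the missing-data rule and what 15.5 reports for SOFA.
- **Detail is deferred.** Sections 15 and 15.1.3 leave endpoint detail to a separate SAP, which is not among the documents reviewed and may define free days. This limits confidence but does not remove the mismatch in the protocol text.
- **The tables show their own gaps.** Section 15.1.1 requires patient and missing counts, so 3.8 against 6.7 assessed of 12 would itself hint at the shorter duration. This is true for an alert reader, though it leaves the percentages themselves misleading.

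A reader might also infer that the stop rule fixes ventilator status, or that the endpoint list itself prescribes status by visit. Neither is supported: the rule concerns vasopressors only, and the by-visit wording appears in 15.1.5, not in the endpoint list.

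**Conclusion.** The mismatch is established from the text: two quantities named in a secondary objective have no endpoint definition and no stated analysis, and the visit schedule cannot supply them. The compression of vasopressor differences (25 points to about 10 in the illustration) is conditional on tables restricted to patients assessed at each visit and on the assumed medians, exponential shape and absence of deaths. Only the 0% at a rule-triggered end of infusion (barring a restart) and the gap to Day 28 follow directly from the documents. For ventilation, the problem is the gap and the selected denominator.

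It would be tempting to conclude that the trial cannot answer its objective, or that the objective gets no result. The documents do not support that. Mortality and shock reversal are endpoints, Day 28 status is assessed, and the start, stop and death records needed for free days are collected. The consequence is modest: these are descriptive parameters, which the synopsis labels exploratory, in a 48-patient pilot with safety as the primary endpoint. The change is still worth making, because the measure is the sponsor's own and the data largely exist.

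**What to change.** - **Add, without replacing anything.** In 15.1.3 and 15.1.5, add vasopressor-free days and ventilator-free days to Day 28. Derive them from the section 12.8 start/stop records and section 12.10 death times. Count days alive and free of support, assign 0 to patients dead by Day 28, and subtract later episodes where recorded. State how gaps of up to 6 hours, which 11.3.3 does not treat as withdrawal, are counted. Report the median and distribution by arm, with mortality beside them.
- **Keep any by-visit table on a fixed denominator.** Use all treated patients, take status from the start/stop records and show deaths as a separate category.
- **Name time until shock reversal in 15.1.5**, so that its analysis is explicit.
- **Label the timing.** Section 15.5 refers to an analysis already carried out. If free days are added after it, report them as post-hoc under that section and its separate analysis plan.

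**Cost.** Analysis-plan wording and one derivation, mostly from data already collected. Restarts after infusion may need checking in source data: 12.8 does not mention them, and routine concomitant medication recording ends 3 days after infusion (10.7, 12.2). Free days also merge death with duration, and scoring death as 0 is a convention, which is why mortality must be shown alongside.

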15.1 Statistical Methods

15.1.1 General Considerations

The analysis will be computed with SAS Version 9.4 (Copyright© 2013 by SAS Institute Inc., Cary, NC, USA).

Unless otherwise specified, baseline is defined as the last planned assessment prior to first dosing and no subgroup analysis is currently planned.

Missing safety, pharmacodynamic, pharmacokinetic and clinical data will not be replaced and will be treated as missing from summary and statistical analyses.

Unless otherwise specified, all treatment comparisons will be two-sided and significance will be assessed at the 5% level.

All safety, pharmacokinetic, pharmacodynamic and clinical data will be summarised by treatment group (Placebo, Dose level 1, Dose level 2 and Dose level 3), and visit, as appropriate.

Qualitative variables will be presented using the number of patients, the number of missing values, the frequency and the percentage per modality.

Quantitative variables will be reported using the number of patients, the number of missing values, the mean, the standard deviation, the median, the first and the third quartiles, the minimum and the maximum.

Between groups comparisons are calculated using an independent t-test or ANOVA-test for quantitative variables with a parametric distribution, or Mann-Whitney test or Kruskal Wallis-test for variables with a non-parametric distribution.

Data is tested for normality using Kolmogorov-Smirnov-test.

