15.5 Retrospective Collection of Data and Post-hoc Analysis

For exploratory analyses of nangibotide's efficacy for the treatment of septic shock, additional data will be collected on the following parameters:

- SOFA score: For all surviving patients, SOFA scores will be collected up to day 5. The purpose of this is to replace data that have been treated as missing in the original analysis.
- Duration of ICU stay: This is expected to provide efficacy data on a clinically relevant endpoint.

These data have not been collected in the original eCRF. They will be collected from source data at sites to the extent available.

The analysis of this data will follow the principles of the main analysis and will be further specified in a separate statistical analysis plan. The results will be reported separately.

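### The protocol describes SOFA by group and visit with no change from baseline or baseline adjustment specified, so at 12 per arm chance differences in entry severity tend to carry into the organ-dysfunction endpoint

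*Combined protocol and SAP*

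**What the plan says.** Section 15.1.3 lists "Resolution of organ dysfunction (SOFA score total and individual domains" among the clinical parameters. They sit under the secondary endpoints there and are labelled exploratory in the synopsis. No rule for resolution, time point or summary measure is given.

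The Clinical Analyses paragraph of 15.1.5 covers the SOFA total and sub-scores in the same sentence as other clinical measures, ending "the vasopressor use, the mechanical ventilation and intubation will be described by treatment group and visit", and adds that "Standard descriptive statistics will be used". The sentence "Changes from baseline will be described" also appears in 15.1.5, but it closes the paragraph on laboratory values, vital signs, ECG and exposure, which does not name SOFA.

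Section 15.1.1 gives the general rules: "Between groups comparisons are calculated using an independent t-test or ANOVA-test for quantitative variables with a parametric distribution" (rank tests otherwise), and "all treatment comparisons will be two-sided and significance will be assessed at the 5% level". No covariate is named. The same section says "baseline is defined as the last planned assessment prior to first dosing", and 11.3.1 schedules a SOFA score on Day 0 before study drug. The baseline characteristics in 15.1.4 include APACHE II but not SOFA. Section 15.3 describes no stratification by severity.

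Section 15.5 adds retrospective SOFA data up to Day 5 for exploratory efficacy analysis and says "The analysis of this data will follow the principles of the main analysis". Sections 15, 15.1.3 and 15.5 leave further detail to statistical analysis plans whose text is not in the documents.

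**The concern.** Resolution is movement away from a patient's own starting state. Group means of SOFA at each visit combine two things: how ill the group was at entry and how much it recovered. In small arms, a dose group that happens to enter less ill will tend to look better later even if the drug does nothing, and a sicker group will tend to look worse. Any comparison made under the general rules of 15.1.1 would be unadjusted and carry the same mixture.

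Sections 6.3 and 8.5.1 say the data from this study will help design later ones, and 15.5 collects the extra SOFA scores specifically to explore efficacy. What is at stake is a misread dose signal and precision given up unnecessarily. No error rate is affected.

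**Working it through.** **Arm size.** Stage 1 has three cohorts of 3 active and 1 placebo; stage 2 has 9 per group (10.3, Tables 5 and 6). Each dose has 3 + 9 = 12 and placebo has 3 × 1 + 9 = 12. The total is 4 × 12 = 48, which reproduces the figures in 15.2.

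**Assumptions.** The documents give no SOFA SD and no correlation between baseline and later scores. I take SD = 2, 3 or 4 points, the same at baseline and follow-up, and rho from 0.3 to 0.7.

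**Chance difference at entry, one dose against placebo.** SE = SD × √(2/12) = 0.408 × SD, which is 0.82, 1.22 and 1.63 points. The chance of a difference of 1 point or more is 2 × [1 − Φ(1/SE)] = 22%, 41% and 54%.

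**How much carries forward.** With no drug effect, a baseline difference d gives an expected follow-up difference of rho × d. An expected shift of 1 point therefore needs a baseline difference of 1/rho: 2.0 points at rho 0.5 and 3.33 points at rho 0.3. The chance that at least one of three doses differs from the shared placebo group by that much was obtained by simulating four arm means, each with SE = SD/√12:

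| Assumed SD | rho 0.3 | rho 0.5 |
|---|---|---|
| 2 | below 1% | 4% |
| 3 | 2% | 24% |
| 4 | 10% | 47% |

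For a single dose-placebo pair at SD 3 and rho 0.5, the closed form is 2 × [1 − Φ(2/1.22)] = 10%.

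**Variance of the dose-placebo contrast, relative to the unadjusted score at a visit.** The change score gives 2(1 − rho); baseline adjustment gives 1 − rho².

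| rho | Unadjusted | Change score | Baseline-adjusted |
|---|---|---|---|
| 0.3 | 1 | 1.40 | 0.91 |
| 0.5 | 1 | 1.00 | 0.75 |
| 0.7 | 1 | 0.60 | 0.51 |

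Adjustment lowers the variance by 9%, 25% and 49%, ignoring the small cost of estimating one slope. The change score beats the unadjusted score only if rho exceeds 0.5.

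**Leftover shift.** Take d = 1.5 points (0.5 SD at SD 3). The unadjusted difference is shifted by rho × 1.5 = 0.45, 0.75 and 1.05 points at rho 0.3, 0.5 and 0.7. The change score is shifted the other way, by (rho − 1) × 1.5 = −1.05, −0.75 and −0.45. Under this linear model, baseline adjustment removes the expected shift.

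**The case against.** **The SAP may already cover this.** Sections 15 and 15.1.3 defer the analysis detail to it, and 15.5 promises a separate plan. This stands as a limit on the point. A reader might infer that the trial is committed to an unadjusted SOFA analysis, and the documents do not support that. They show only that the protocol specifies neither a change score nor an adjustment.

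**Imbalance would be visible.** Pre-dose SOFA should appear in the by-visit tables, and APACHE II is tabulated at baseline. That is a partial safeguard: a reader could see a difference at entry but could not correct for it from group means.

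**The endpoint is exploratory.** Safety is primary, 15.2 calls the study exploratory, and only description is planned for SOFA. This stands and limits the weight of the point. The improvement is still nearly free.

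**Missing scores matter more.** Under 11.3.3 the end-of-treatment assessments are done once when infusion stops early, 15.1.1 leaves missing values unreplaced, and the data added under 15.5 cover survivors, to the extent available in source records. This stands too. Baseline adjustment does not repair it, and an adjusted interval based on survivors could look firmer than it is. The precision gain applies only to patients who contribute a score.

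**Conclusion.** The point holds as a gap in the protocol text. The endpoint is named as resolution, but no change from baseline and no baseline adjustment is specified for SOFA. A covariate already collected before dosing would give a better estimate. The size depends entirely on the assumed SD and rho: the chance of an expected shift of 1 point or more in at least one dose group runs from below 1% (SD 2, rho 0.3) to 47% (SD 4, rho 0.5).

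Three stronger readings should be resisted:

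- A group that enters less ill need not show lower SOFA at every visit. Only rho times the entry difference is expected to persist.
- The chance that at least one dose differs from placebo at entry by 1 point or more is 47%, 75% or 87% at SD 2, 3 or 4. Those figures describe baseline differences for the worst of three comparisons, not distortion of the result.
- This is not systematic bias. Randomisation makes the expected imbalance zero; the issues are chance imbalance and lost precision.

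**What to change.** In 15.1.5 and in the analysis plan promised by 15.5:

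1. For SOFA total and each domain, at each planned day, estimate each dose-minus-placebo difference with a 95% CI from a linear model with treatment and Day 0 pre-dose SOFA as terms.
2. Describe change from baseline alongside it. The adjustment is the operative step. With baseline in the model, analysing change or the follow-up score gives the same treatment contrast, and a change score alone is not a sufficient remedy.
3. Show the number contributing and the deaths by arm and day.
4. Label the estimates as exploratory and conditional on patients being alive with a score.

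The cost is plan wording, one model term and two rows in a table. Day 0 SOFA is already scheduled and baseline is already defined, so no new data or visits are needed.

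### Time until shock reversal is given no rule for death before reversal; under the general rules, deaths in shock drop out and arms are compared among reversers only

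*Combined protocol and SAP*

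**What the plan says.** Section 15.1.3 places this among the clinical parameters under the secondary endpoints: "Time until shock reversal defined as cessation of vasopressor support for 24 hours". The synopsis labels the clinical parameters exploratory. Mortality at Days 28 and 90 is a separate item in the same list.

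The rules that reach this endpoint are the general ones in Section 15.1.1:

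- "All safety, pharmacokinetic, pharmacodynamic and clinical data will be summarised by treatment group". For quantitative variables this means n, number missing, mean, SD, median, quartiles, minimum and maximum.
- "Between groups comparisons are calculated using an independent t-test or ANOVA-test for quantitative variables with a parametric distribution", with Mann-Whitney or Kruskal-Wallis otherwise.
- "Unless otherwise specified, all treatment comparisons will be two-sided and significance will be assessed at the 5% level".
- "Missing safety, pharmacodynamic, pharmacokinetic and clinical data will not be replaced and will be treated as missing from summary and statistical analyses".

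The Clinical Analyses paragraph of Section 15.1.5 covers sepsis-related events and SOFA scores, and adds that "the vasopressor use, the mechanical ventilation and intubation will be described by treatment group and visit". It closes with "Standard descriptive statistics will be used". Time until shock reversal is not in its list.

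The supplied text gives no time origin for this endpoint, no censoring rule, no rule for death before reversal, and no Kaplan-Meier, log-rank, Cox or competing-risk method. Sections 15 and 15.1.3 leave further detail to a separate SAP, which is not among the documents.

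**The concern.** Shock reversal is a time-to-event outcome in a population where a sizeable share of patients may die before the event. A patient who dies on vasopressors never has a reversal time. If the empty field is handled under the general missing-data rule, that patient leaves both the summary and the test.

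The remaining patients are defined by something that happened after randomisation and that treatment may change. If the drug keeps some patients alive who then come off vasopressors, they enter the treated average and have no counterpart in the placebo average. The difference in means or medians then mixes any effect on speed with a change in who is counted. A rank test on the same patients has the same fault.

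Effects on clinical parameters are a stated secondary objective (Section 7). The results are meant to help design later studies (Sections 6.3 and 8.5.1), and the unblinded Day 28 analysis may inform business decisions (Section 15.4). A reversal-time table that points the wrong way could mislead those readers.

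**Working it through.** **The plan's own figure.** Section 15.2 gives 48 patients, 12 per group, without a power calculation. From Tables 5 and 6, each dose has 3 + 9 = 12 patients and placebo has 3 × 1 + 9 = 12, so 4 × 12 = 48. The figure reproduces. No effect size, SD or event rate is stated, so the inputs below are assumptions.

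**Inputs.** The only mortality figure in the documents is almost 30% for severe sepsis (Section 6.1, background). I use 30% as an assumed placebo risk of death in shock, with a range of 20% to 40%. I assume that the drug halves it and that all other patients reverse by Day 28. The comparison is one dose group against placebo.

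**Check 1, closed form.** Let patients who would reverse on either arm average 2.5 days, and let rescued patients average m days. With deaths dropped, the placebo mean is 2.5 days and the treated mean is (0.70 × 2.5 + 0.15 × m) / 0.85.

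| m (days) | Treated mean (days) | Placebo mean (days) | Reversed, treated vs placebo |
|---|---|---|---|
| 2 | (1.75 + 0.30)/0.85 = 2.41 | 2.50 | 85% vs 70% |
| 2.5 | (1.75 + 0.375)/0.85 = 2.50 | 2.50 | 85% vs 70% |
| 5 | (1.75 + 0.75)/0.85 = 2.94 | 2.50 | 85% vs 70% |

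The drug does the same good in all three rows, yet the comparison among reversers makes it look faster, neutral or slower. At m = 5, the other treated reversers would need a mean of (0.85 × 2.5 − 0.75)/0.70 = 1.96 days, about 0.54 days faster, for the treated mean merely to equal placebo.

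**Check 2, a different shape.** Take log-normal times with log-SD 0.6 and a median of 48 h in patients who reverse on either arm. Their mean is 48 × exp(0.6²/2) = 57.5 h. If rescued patients have a median of 96 h, their mean is 114.9 h.

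- Deaths dropped: the treated mean is (0.70 × 57.5 + 0.15 × 114.9)/0.85 = 67.6 h against 57.5 h. The simulated medians are 53.5 h against 48.0 h.
- All patients kept, death as a competing event (simulated): 75.2% against 65.6% reversed by 120 h, and 85% against 70% by Day 28.
- Range of the treated mean with deaths dropped (placebo stays at 57.5 h): 57.5 h if rescued patients have the usual 48 h median; with 96 h, 63.8 h at 20% vs 10% deaths and 71.9 h at 40% vs 20%; with 144 h, 86.3 h at 40% vs 20%.
- If the drug also shortens every treated reversal time by 10%, the central treated mean is 0.9 × 67.6 = 60.8 h, still above placebo.

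**Check 3, at the planned size.** With 12 per group and the central case, 12 × 0.70 = 8.4 placebo and 12 × 0.85 = 10.2 treated patients are expected to have a reversal time. In simulation the treated arm has the longer observed mean in about 69% of trials and the longer observed median in about 62%, against about 50% with no bias. With a 96 h median for rescued patients, the figure for the mean is 63% at 20% vs 10% deaths and 74% at 40% vs 20%. It returns to about 50% when rescued patients reverse at the usual speed. The proportion reversed by Day 28 ranks the treated arm worse in about 13% of trials. The reference there is about 41% when the arms have equal deaths, because ties are common.

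**The case against.** Several points on the other side are sound.

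- A reader might infer from Section 15.1.5 that the plan prescribes descriptive statistics only for this endpoint. The documents do not support that: the paragraph does not name it, a duration per patient is not a by-visit measure, and Section 15.1.1 also provides between-group tests. Those tests would share the fault if deaths are dropped.
- A reader might infer that the plan states a rule excluding deaths in shock. It does not. Exclusion is the literal result of having no reversal time under the missing-data rule. The unseen SAP may censor these patients or count them as not reversed.
- A reader might infer that the analysis is biased against an effective drug. The direction depends on when rescued patients reverse. There is no bias in the mean if they reverse at the average speed, and the drug is flattered if they reverse sooner.
- Background severe-sepsis mortality is not the risk of dying before reversal in this trial. Deaths after reversal do not leave the summary. The 30% is an assumption only.
- Safety is primary, mortality is tabulated separately, and Section 15.1.1 requires the number missing for each variable, so an attentive reader would see that patients had dropped out.

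These points narrow the finding and limit its consequence. They do not make a comparison among reversers a valid randomised comparison, whichever way it errs. The missing-data default has also already been revisited for another clinical parameter: Section 15.5 collects further SOFA scores to fill values analysed as missing. That repair does not extend to shock reversal.

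**Conclusion.** The point holds as a gap in the supplied text whose stated default is unsuitable for this endpoint. No rule covers death before reversal, and the general rules, applied as written, compare arms among reversers only. Under the assumptions in the first check the treated mean ranges from 2.41 to 2.94 days against 2.50 on placebo, while the true proportions reversed stay at 85% and 70%. Neither the sign nor the size can be known in advance, because both depend on assumed deaths in shock and on how quickly rescued patients reverse.

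The consequence is limited: the endpoint is not primary, the study is an unpowered pilot with 12 per group, and mortality is shown beside it. The conclusion is about the protocol text; the separate SAP could already resolve it.

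**What to change.** In the SAP:

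1. Define the time origin. Section 8.1 allows up to 24 hours between shock onset and study drug, so the choice matters on this time scale.
2. Analyse reversal as cumulative incidence to Day 28 by arm, with death before reversal as a competing event and survivors still on vasopressors censored at Day 28.
3. Report by arm the proportion reversed and the number who died before reversal.
4. Do not compare mean or median times among reversers only.
5. Where vasopressor-free days are reported (already named in the Section 7 objectives), state how deaths are scored, for example as zero days.

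No new data should be needed: the start and end of vasopressor therapy (Section 12.8) and the date and time of death (Section 12.10) are already recorded. The cost is a little extra analysis work. If the main SAP is already final, the further SAP that Section 15.5 calls for could carry the analysis, labelled post hoc.

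Estimates will be imprecise. For 85% against 70% with 12 per group, the standard error of the difference is √(0.85 × 0.15/12 + 0.70 × 0.30/12) = 0.168, about 17 points for a 15-point difference, so the result should be read as descriptive.
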